HIV-associated neuropathic pain (HIV-NP) affects a significant proportion of people living with HIV (PLWH) and has a major impact on everyday functioning and quality of life in this population. Over the past decade a growing number of preclinical studies and clinical trials have indicated that cannabis administration and manipulation of the endocannabinoid (EC) system may have therapeutic utility in addressing HIV-NP. EC CB2 receptor activation and inhibition of the EC deactivation enzymes fatty acid amide hydrolase (FAAH) and monoacylglycerol lipase (MAGL) have been shown to decrease pain in rodent models of HIV-NP, while acute exposure to cannabis reduces self-reported pain in PLWH with neuropathy. However, little work has been conducted to elucidate the effects of the two primary cannabinoids (delta-9-tetrahydrocannabinol, THC and cannabidiol, CBD) on the EC system or to assess EC function in PLWH. The objective of this application is to address these fundamental gaps in our knowledge by: 1) examining the acute effect of administering NIDA-prepared THC/CBD products on HIV-NP; 2) utilizing mHealth text messaging to monitor daily real-world self-administered cannabis effects on pain; 3) assessing the relationship between cannabinoids and EC biomarkers, including ligands, enzymes, and receptor expression; and 4) conducting exploratory analyses to evaluate the effect of longitudinal cannabinoid use on changes in HIV-NP over time. We will examine the effect of low (0.01%), medium (one vial of 5.1%), and high dose (two vials of 5.1%) CBD-containing cannabis on NP, the EC system, and heart rate variability (as a proposed objective biological measure of pain) in 100 PLWH who use cannabis to treat neuropathic pain. We will subsequently employ a mobile phone text messaging system, the Individual Monitoring of Pain And Cannabis Taken (IMPACT), to track cannabis exposure, CBD and THC consumption, and pain over a period of 6 months in these same PLWH participants. IMPACT will be used to quantify the real-time effects of acute CBD/THC exposure on pain before and after cannabis self-administration, the real-time relationship between self-reported pain and changes in HRV, and to assess any longitudinal changes in NP, HIV clinical outcomes (viral load, CD4) and cognition during the 6-month period. This plan allows us to acquire data and compare the effects of cannabis product obtained from NIDA and self-administered cannabis obtained from local medicinal dispensaries. The overarching hypothesis is that CBD exposure and a higher CBD/THC ratio will exert beneficial effects both in the laboratory and during the observational study, including increasing EC biomarkers and reducing NP. In summary, this approach will advance our understanding about several key issues, including the interaction between cannabis constituents, the EC system and pain, the biological mechanisms that underlie these effects (EC enzymes, receptor), and the longer-term effects of cannabis use on health-related outcomes in HIV, including predictors of mortality (HRV, CD4, viral load) and neurocognition.

SCHEMA

Effect of Cannabis Administration and Endocannabinoids on HIV Neuropathic Pain

DESIGN: Our objective is to assess PLWH who have neuropathic pain and are currently using cannabis, including light use (1-4 times per month) and heavy use (5+ times per month). These participants will be enrolled in a study that consists of two stages: Stage 1) PLWH will participate in a 6-month mHealth text messaging program (Individual Monitoring of Pain and Cannabis Taken, or IMPACT) that will examine the association between cannabis obtained from local dispensaries and changes in daily pain. Participants will return for a visit after 6 months for follow-up testing so we can examine longitudinal changes in neuropathic pain, neuropsychological performance and EC function. Stage 2) A double blind crossover study where we administer three different doses of vaporized cannabis to each participant that contain THC and varying concentrations of CBD (low, medium, high), including: a) 2 vials of 0.01% CBD + 1.9% THC, b) 1 vial of 0.01% CBD + 1.9% THC and 1 vial of 5.1% CBD + 1.4% THC, and c) 2 vials of 5.1% CBD + 1.4% THC. Here we will examine the acute effects of cannabis obtained from NIDA on pain intensity, blood endocannabinoid (EC) levels, and the relationship of pain with heart rate variability (HRV).

POPULATION: PLWH with neuropathic pain and current cannabis use.

STRATIFICATION: none

REGIMEN OR INTERVENTION

Three doses of cannabis (with varying concentrations of CBD) administered once per day on three separate days.

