Endocannabinoids reduce pain and modulate neuronal activity at synapses throughout pain processing pathways, but the effect of cannabis on the EC system is understudied¹³. The EC system includes two receptors, CB1 and CB2, and two primary ligands, N-arachidonylethanolamine (AEA) and 2-arachidonoylglycerol (2-AG), which are deactivated by the enzymes fatty acid amide hydrolase (FAAH) and monoacylglycerol lipase (MAGL), respectively^{14, 15}. EC ligands act as a negative feedback system that inhibits the release of pro-inflammatory cytokines and reduces neuronal signaling in response to pain^{13, 15, 16}. Elevated

peripheral levels of AEA and 2-AG occur in preclinical pain models¹³ and FAAH and MAGL inhibitors produce antinociceptive effects in rodent models of acute and chronic pain^{17, 18}. Mice lacking CB2 receptors also show enhanced pain responses to sciatic nerve ligation¹⁹. Despite the reported benefits of acute cannabis treatment for pain, chronic cannabis use may disrupt EC function²⁰. Heavy cannabis use (several days per week) reduces EC ligand levels²¹ and CB1 and CB2 expression in both humans and mice²²⁻²⁵. Psychotic patients with heavy cannabis use exhibited decreased CB2 and increased FAAH in peripheral blood mononuclear cells (PBMC) compared to healthy controls²², while increased AEA in cannabis-naïve schizophrenia patients was completely blocked by cannabis use²⁰. Cannabis use may disrupt EC function, but little is known about the specific effects of THC and CBD. One study in schizophrenia patients reported that 4 weeks of administered CBD increased plasma AEA and reduced FAAH²⁶. Preclinical and *in vitro* data show that CBD may increase AEA expression by inhibiting both neuronal uptake and FAAH activity²⁷. In contrast, THC, but not CBD, is a strong CB1 and CB2 receptor agonist^{28, 29} and could represent the primary cannabis constituent that disrupts EC function. Overall, these data suggest that THC and CBD may have differential effects on EC activity, a question that requires investigation in a real-world setting of chronic cannabis use.

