2.0 STUDY DESIGN

Our objective is to assess 100 community-dwelling PLWH with neuropathic pain (PLWH-NP) who are recruited and tested at the HIV Neurobehavioral Research Program (HNRP)/Center for Medicinal Cannabis Research (CMCR) facilities located at the UCSD Medical Center. These participants will be enrolled in a study that consists of two stages: 1) administration of three different doses of vaporized cannabis obtained from NIDA (one dose per day on three separate days) that contain THC and varying concentrations of CBD, including: a) 2 vials of 0.01% CBD + 1.9% THC, b) 1 vial of 0.01% CBD + 1.9% THC and 1 vial of 5.1% CBD + 1.4% THC, and c) 2 vials of 5.1% CBD + 1.4% THC; 2) participation in a 6-month text message monitoring study, the Individual Monitoring of Pain and Cannabis Taken (IMPACT), where pain and cannabis use from local dispensaries is tracked. We will use a randomized crossover design where all participants receive each of the three cannabis doses at the HNRP and then are subsequently enrolled into IMPACT. We will recruit individuals who are currently using cannabis at least once a month to treat pain. The primary outcome measures of the study will examine: 1) the acute effects of NIDA-obtained cannabis on pain, EC levels, and the relationship with HRV (Aim 1); 2) the association between dispensary-obtained cannabis and changes in pain reported via IMPACT (Aim 2); 3) the effect of chronic THC and CBD exposure on longitudinal changes in pain, EC measures, and neurocognitive performance (Aim 3). Secondary and exploratory analyses will compare NIDA-obtained and dispensary-obtained cannabis effects on neuropathic pain and evaluate if there are different effects of reported cannabis strain (Sativa, Indica), specific cannabis products (e.g., OG Kush, Sour Lemon, etc.), or mode (smoking, vaporizing, ingesting food product) on pre-post drug exposure changes in pain

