7.3 Aim 3 Measures and Analyses

We will use a linear model to examine the association between the total CBD, THC, and CBD/THC ratio during IMPACT and the change in NP, disease markers (CD4, viral load, Total Neuropathy Score, and neurocognitive global T-score), and EC biomarkers (AEA, 2-AG, FAAH, MAGL, CB2) from baseline to the final visit after month 6. We will control for confounders as in Aims 1 and 2, including any CBD and THC levels recorded at the baseline and final sessions. Linear models will compare the month 6 – baseline change in pain and in EC biomarkers between the heavy- and light-cannabis groups. One exploratory analysis will test for an interaction between group (light vs. heavy) and CBD and THC levels on change in NP and EC biomarkers. We will assess if exposure mode (smoking/vaporizing/ingestion) predicts pain outcome. We will examine if there is an association between pain change over time and changes in EC biomarkers. During the 6-month IMPACT, alterations may occur in cannabis use or pain medication (e.g., a person enrolled as a light cannabis user may start to engage in heavy use or begin using non-cannabis medication for pain, i.e., an opiate, which we will record with IMPACT). To address these issues we will conduct light vs. heavy use analyses based both on the baseline group classification and the actual use during IMPACT, include a cannabis use 'change' factor in the analyses (going from light to heavy use, or vice versa), and include the initiation of any non-cannabis pain medication as a factor in the model.

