For Aim 2, with 20% attrition over the 6 months of IMPACT we have $n= 80$ participants with 6 months (26 weeks) of data. We conservatively ignore the drop-out participants (who nonetheless contribute partial data). Assume, conservatively, that participants will use cannabis on average 2 times/week. This gives $n=80$ and $k=52$ observations/participant. If ICC is the intra-class, or within-participant correlation, the effective sample size (number of equivalent independent observations) is $n_{\text{eff}} = n/(ICC+(1-ICC)/k) \approx n/ICC$ [e.g., Killip, Mahfoud, Pearce, Ann Fam Med, 2004; 2:204-208.]. Assuming conservatively $\rho=0.5$ (or lower), we get $n_{\text{eff}} = 2n = 200$ [$n_{\text{eff}} = 160$]. We have 80% power to detect a (partial) correlation R between the individual predictors (Hypothesis 1: CBD, THC, and the CBD/THC ratio; Hypothesis 2: pain levels and HRV) and change in pain of $R = 0.218$ (or semi-partial $R^2 = 0.0475$), after adjusting for confounders. Calculations used G*Power.

For Aim 3, assuming $n = 80$ participants complete the 6-month follow-up, we have 80% power to detect an association between an individual predictor and response (e.g., total CBD and changes in neuropathic pain levels) of $R = 0.302$ (or semi-partial $R^2 = 0.092$), after adjusting for confounders. The calculations used G*Power.

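### The light/heavy cut at 5 uses a month does not match the heavy use cited in the background, and dichotomising there costs the Section 7.3 frequency comparison power through dilution or imbalance

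*Combined protocol and SAP*

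**What the plan says.** The Schema defines the two classes: "including light use (1-4 times per month) and heavy use (5+ times per month". Section 2.0 sets the recruitment floor: "We will recruit individuals who are currently using cannabis at least once a month to treat pain". The Schema also has the line "STRATIFICATION: none". The documents give no reason for the cut and no expected light:heavy split.

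Section 1.1 uses the same term for a different frequency: "Heavy cannabis use (several days per week) reduces EC ligand levels". In Section 7.4 the Aim 2 sample size argument reads: "Assume, conservatively, that participants will use cannabis on average 2 times/week".

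The classes are used in three places. In Section 7.3: "Linear models will compare the month 6 – baseline change in pain and in EC biomarkers between the heavy- and light-cannabis groups". The same section adds that "we will conduct light vs. heavy use analyses based both on the baseline group classification and the actual use during IMPACT", and includes a factor for moving from light to heavy or back. Section 7.2 uses light versus heavy as a predictor of the change in HRV between the first and last week. Section 7.1 lists it among many candidate covariates. Section 7.3 separately models total CBD, total THC and their ratio during IMPACT; those models do not use the cut.

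**The concern.** Someone who uses cannabis five times a month, little more than weekly, is in the same class as someone who uses it daily. The only frequency the documents link to lower EC ligands is several days per week, well above the threshold. If many in the heavy class use less than that, the group difference is diluted. If use is generally high, few participants are left in the light class and the comparison is imprecise for that reason.

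The interpretation of the Section 7.3 comparison is at stake. A null difference between classes split at 5 uses a month could easily be read as evidence that frequent use does not alter pain or EC biomarkers, which this contrast is poorly placed to show. The change factor has a related weakness, because moving from 4 to 5 uses a month counts as a change of class.

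**Working it through.** **Units.** Planning average (Section 7.4): 2 × 52/12 = 8.7 uses a month. Heavy threshold (Schema): 5 × 12/52 = 1.15 a week. Several days per week is not defined; read as 3 to 5 days with one use a day, it is 13 to 21.7 uses a month. The heavy class then starts at 5/21.7 = 23% to 5/13 = 38% of that frequency.

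**The plan's own figure.** Section 7.4 gives 80% power for R = 0.302 at n = 80 in Aim 3. For a single coefficient, f² = R²/(1 − R²) and the noncentrality is √(n f²). Here f² = 0.0912/0.9088 = 0.1004 and √(80 × 0.1004) = 2.83. With a two-sided 5% test, power is 0.799, so the figure reproduces. (The 5% level is in Section 7.1; sidedness is not stated.) It is for an individual predictor such as total CBD and serves here only as a yardstick.

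**Loss through the indicator.** If the outcome correlates R with frequency, and class matters only through frequency, the correlation with the indicator is R × corr(indicator, frequency). The documents give no use distribution. Two were assumed, both with mean 8.7 a month: geometric, and log-normal with log-SD 0.8.

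| | Geometric | Log-normal |
|---|---|---|
| Light (below 5 a month) | 38.7% | 38.4% |
| Share of heavy class below 13 a month | 62% | 70% |
| Correlation of indicator with log frequency | 0.830 | 0.788 |
| Power if effect follows log frequency | 63% | 58% |
| Correlation of indicator with raw frequency | 0.617 | 0.536 |
| Power if effect follows raw frequency | 39% | 31% |

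Example: 0.302 × 0.830 = 0.251; f² = 0.0628/0.9372 = 0.0670; noncentrality √(80 × 0.0670) = 2.32; power 0.63.

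**Sensitivity to the mean.** The figure of 2 a week may be too low, so higher means were tried with the geometric and with log-normals of log-SD 0.5, 0.8 and 1.1, in whole uses per month.

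| Mean uses a month | Light | Power, log frequency | Power, raw frequency |
|---|---|---|---|
| 8.7 | 14–48% | 43–63% | 23–39% |
| 13 | 3–34% | 19–60% | 10–29% |
| 17.3 | 1–25% | 10–57% | 6–24% |

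Power does not recover as use rises; the cause shifts from dilution to imbalance. In a plain two-group comparison with 80 completers, the difference detectable with 80% power is d = 0.63 at 40:40, 0.69 at 24 light to 56 heavy, 0.79 at 16:64 and 1.06 at 8:72.

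**Change factor.** If monthly counts are Poisson, a person at a constant 4 a month records 5 or more in 37% of single months, and one at a constant 5 records 4 or fewer in 44%. Averaging over six months would lessen this, but Section 7.3 does not state the window.

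**The case against.** A reader might infer that the trial's EC hypothesis rests on heavy use several days per week, so that a null light-versus-heavy result would leave it untested. The documents do not support that. The overarching hypothesis concerns CBD exposure and the CBD/THC ratio, Section 2.0 frames Aim 3 around chronic THC and CBD exposure, and Section 7.3 already models total CBD, total THC and their ratio without the cut. The frequency in Section 1.1 is one background sentence. This objection stands and limits the point to the frequency contrast.

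A reader might also infer that the contrast mostly sets occasional users against moderate ones. The 2 uses a week is a conservative Aim 2 input, not a forecast. Even at that mean, the heavy class averages about 2.8 to 2.9 uses a week under the two main assumed distributions. At 4 a week, only 38–45% of the heavy class under those distributions falls below 13 a month. An average user in the heavy class does not by itself prove dilution. This stands too, although higher use brings imbalance instead.

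Further, the plan claims no power for light versus heavy, the 13-a-month benchmark is a reading of an undefined phrase, and days per week are not the same unit as times per month. The stratification line is weak evidence on recruitment quotas, since every participant receives all three doses. None of this supplies a reason for the cut or restores the lost information. The CBD and THC models do not replace a frequency analysis, because none uses frequency as such.

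**Conclusion.** The point holds for the light-versus-heavy analyses in Section 7.3, their change term, and the HRV predictor in Section 7.2. The cut is unexplained and lies well below the frequency in Section 1.1. In every case tried the indicator loses power: from 80% to at most about 63% if the effect follows log frequency, and at most about 39% if it follows raw frequency, with much lower values where the light class is small. These figures assume n = 80, a two-sided 5% test, the stated use distributions, and an effect linear in frequency or its log. The direction is consistent; the size is not fixed by the documents. The stated power figures in Section 7.4 do not depend on the cut. The total CBD and THC models and the overarching hypothesis are unaffected.

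**What to change.** In Section 7.3, and for the HRV predictor in Section 7.2, pre-specify use frequency as a continuous predictor for the main frequency analysis: log(1 + uses per 30 days).

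- IMPACT version: 30 × events divided by days with a response. Section 7.2 expects 80–90% of texts to be answered, so a raw count would understate use in poor responders. Adding 1 keeps the measure defined for anyone with no use.
- Baseline version: the same measure where uses per month were recorded as a number. Section 4.3 mentions only an assessment of substance use, so where only the class was recorded, keep the class for the baseline version.
- Change term: the difference between the two values of this measure, where both exist.
- Light versus heavy: report as secondary, with actual group sizes, and state that a null result there is not evidence about use on several days per week.

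The cost is SAP wording; eligibility and dosing do not change. The coding should be settled before the data are analysed, since choosing it afterwards would be post hoc. The downsides are that a slope is less simple to present than a two-group difference and that it assumes a roughly linear effect on the log scale.

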1.0 INTRODUCTION

HIV-associated neuropathic pain (HIV-NP) affects a significant proportion of people living with HIV (PLWH) and is one of the leading causes of disability in this population. Acute cannabis administration is reported to alleviate HIV-NP, but we have limited knowledge about the effects of cannabis constituents (THC and cannabidiol/CBD), the consequences of long-term cannabis use, and the impact of cannabis on endocannabinoid (EC) function in PLWH. Our objective is to address these three fundamental gaps in our knowledge by: 1) examining the acute effects of various CBD/THC products on HIV-NP, 2) utilizing a mHealth text messaging protocol (Individual Monitoring of Pain and Cannabis Taken or IMPACT) to monitor daily real-world cannabis use and changes in pain; 3) studying the relationship between cannabinoids, EC biomarkers, and chronic neuropathic pain.

1.1 Background

HIV-related neuropathic pain (HIV-NP) represents a significant problem for PLWH. HIV sensory neuropathy (HIV-SN), typically characterized by sensory deficits, numbness, tingling, or pain in feet or hands, is a common health concern in people living with HIV (PLWH)¹. HIV-SN is often associated with neuropathic pain (NP) described as “stabbing”, “burning” or “aching” that is the most frequent source of HIV-SN disability², while the prevalence of reported pain in PLWH ranges from 27 to 97%³. A large scale study by our group indicated that 57% (881 out of 1539 PLWH) exhibited HIV-SN and 38% reported HIV-NP⁴. Treatment of HIV-NP remains difficult; a 2010 review indicated that only capsaicin, human nerve growth factor, and smoked cannabis showed superior pain reduction compared to placebo⁵. Studies at the University of California Center for Medicinal Cannabis Research (CMCR) indicate that 34-40% of patients exposed to cannabis cigarettes with delta-9-tetrahydrocannabinol (THC) exhibited significant pain reduction compared to 17-20% on placebo⁶⁻⁸. While THC doses in the 1.3% to 3.5% range alleviate pain for some participants, higher doses of THC (7-8%) did not provide additional benefit for pain reduction⁸ or actually increased capsaicin-induced pain in healthy volunteers⁹. Importantly, combined cannabidiol (CBD)/THC extracts are reported to be more effective at treating pain compared to THC alone in human cancer-related pain and in rodents^{10, 11}. CBD exhibits antioxidant and neuroprotective properties, inhibiting the release of inflammatory cytokines such as TNF α ¹². However, the optimal THC/CBD ratio for effective pain treatment is not yet known. There may also be discrepancies between data obtained from controlled clinical trials and the use of unregulated cannabis obtained from dispensaries. There is thus a clear need to close the gap between existing clinical data and real-life cannabis use from public sources, including the effects on the endocannabinoid (EC) system and NP.

Endocannabinoids reduce pain and modulate neuronal activity at synapses throughout pain processing pathways, but the effect of cannabis on the EC system is understudied¹³. The EC system includes two receptors, CB1 and CB2, and two primary ligands, N-arachidonylethanolamine (AEA) and 2-arachidonoylglycerol (2-AG), which are deactivated by the enzymes fatty acid amide hydrolase (FAAH) and monoacylglycerol lipase (MAGL), respectively^{14, 15}. EC ligands act as a negative feedback system that inhibits the release of pro-inflammatory cytokines and reduces neuronal signaling in response to pain^{13, 15, 16}. Elevated

peripheral levels of AEA and 2-AG occur in preclinical pain models¹³ and FAAH and MAGL inhibitors produce antinociceptive effects in rodent models of acute and chronic pain^{17, 18}. Mice lacking CB2 receptors also show enhanced pain responses to sciatic nerve ligation¹⁹. Despite the reported benefits of acute cannabis treatment for pain, chronic cannabis use may disrupt EC function²⁰. Heavy cannabis use (several days per week) reduces EC ligand levels²¹ and CB1 and CB2 expression in both humans and mice²²⁻²⁵. Psychotic patients with heavy cannabis use exhibited decreased CB2 and increased FAAH in peripheral blood mononuclear cells (PBMC) compared to healthy controls²², while increased AEA in cannabis-naïve schizophrenia patients was completely blocked by cannabis use²⁰. Cannabis use may disrupt EC function, but little is known about the specific effects of THC and CBD. One study in schizophrenia patients reported that 4 weeks of administered CBD increased plasma AEA and reduced FAAH²⁶. Preclinical and *in vitro* data show that CBD may increase AEA expression by inhibiting both neuronal uptake and FAAH activity²⁷. In contrast, THC, but not CBD, is a strong CB1 and CB2 receptor agonist^{28, 29} and could represent the primary cannabis constituent that disrupts EC function. Overall, these data suggest that THC and CBD may have differential effects on EC activity, a question that requires investigation in a real-world setting of chronic cannabis use.

Pain is typically assessed by self-report, but the field would benefit from the use of biological measures sensitive to HIV-NP. Common pain measures include the Visual Analog Scale (VAS), where individuals mark their level of pain on a 10 cm line from “no pain” to “worst pain” and the Numeric Pain Rating Scale (NPRS), a 0-10 scale with similar endpoints⁵. In contrast to self-report, suggested metrics of objective pain such as fMRI neuroimaging remain in development³⁰. Another proposed option, heart rate variability (HRV), is a measure of autonomic function closely related to pain self-report and analgesic efficacy³¹⁻³⁴. HRV quantifies the beat-to-beat variation in heart rate and provides a measure of sympathetic and parasympathetic tone. Healthy individuals exhibit higher HRV, but HRV is significantly lower in PLWH³⁵⁻³⁷, correlates with the level of pain intensity in chronic fibromyalgia³⁸, and improved HRV after biofeedback is associated with less pain on VAS³⁹. Persons with effective analgesic treatment of chronic pain exhibited improved HRV relative to pain sufferers with ineffective treatment³², suggesting HRV may serve as a pain biomarker.

The effects of cannabis on health outcomes and cognition in HIV remain unclear. Despite prevalent cannabis use, there are significant concerns that drug exposure may impair cognition and affect everyday functioning⁴⁰⁻⁴². Chronic cannabis use is associated with cognitive deficits across a wide range of domains (memory, attention, executive function)⁴³⁻⁴⁵, but little is known about the potential neuropathology⁴⁶. Preclinical studies indicate that CBD may have beneficial effects on cognition, including rescuing memory impairment in a mouse model of malaria⁴⁷, improving object recognition in a model of Alzheimer’s disease⁴⁸, and attenuating visuospatial deficits induced by THC in rhesus monkeys⁴⁹, but CBD exposure effects in PLWH are not known. Similarly, the effects of CBD and THC on measures of disease state, such as CD4 level and viral load, are not well understood. Rhesus macaques exposed to THC for 6 months exhibited lower viral load after infection with simian immunodeficiency virus⁵⁰, while daily cannabis use was associated with lower viral load among recently seroconverted PLWH when compared to less frequent use⁵¹. However, THC and CBD exposure was not reported in this study and remains an important and understudied issue in this field.

mHealth text messaging will serve as a useful tool to monitor the relationship between pain and

cannabis use. Text messaging is an effective method to modify health behaviors, monitor substance use, and track pain⁵². Our group has recently demonstrated the feasibility of using short message service (SMS) texting to promote ART adherence and monitor daily methamphetamine (METH) use in PLWH with bipolar disorder or METH dependence, but SMS has not been used to assess cannabis exposure in this population^{53, 54}. There are a variety of cannabis mobile apps providing information on strain and dispensary information, but none that address abuse, addiction, or treatment⁵⁵. Ecological momentary assessment (EMA), the technique of gathering data within a participant's environment using multiple assessments⁵⁶, has been applied to alcohol and cigarette use⁵⁷, but few studies have examined cannabis. We will utilize a novel text messaging protocol, Individual Monitoring of Pain And Cannabis Taken (IMPACT), to assess the relationship between real-world self-administered cannabis and changes in pain symptoms that precede and follow drug exposure.

